Statistical Analysis Plan

We will be looking at changes in outcomes from before to after the MBSR intervention in (a) the MBSR compared to TAU participants, and (b) within the MBSR participants. We will focus on within-persons mean differences using paired samples t-tests within the intervention group. To determine the impact of MBSR on the postoperative TKA outcomes, we will conduct multivariate analyses of variance of conceptually linked dependent variables (i.e. pain variables, mental health variables) with significant results followed up by Tukey post-hoc tests.

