RESEARCH PROTOCOL

The “*What is a Protocol?*” file on the HREB ethics website requested that applicants provide information about both the scientific and ethical aspects of their proposal. We will therefore divide this protocol description into those two sections.

1. Scientific Elements

(a) Background Research

In 2010 - 2011, more than 762,000 total knee arthroplasty (TKA) surgical procedures were performed across Canada (1). This number is expected to increase dramatically in the coming years with the growing older adult population and with the recently quantified TKA projections for younger patients (2). The growth of this procedure has resulted in increasing reports of dissatisfaction and poor outcomes such as increased pain, unmet expectations, reduced daily functioning (3), and compromised psychological health (4). Although suboptimal outcomes are not unusual in surgical procedures, there is a discrepancy in the proportion of poor outcomes associated with TKA compared to other arthroplasties. For example, 18-20% of patients following TKA report dissatisfaction (3, 5) compared to only 7% following a total hip arthroplasty (6). In response to these discrepant findings, there have been a significant number of studies that have identified psychological and psychosocial factors that are implicated in poor outcomes of TKA, even when controlling for medical factors such as surgical technique (7). This is not surprising given that more than 50% of adults undergoing TKA suffer from osteoarthritis, which has high comorbidity rates with mental disorders (8). Although psychological factors have been identified as contributing to poor outcomes, it is not clear whether an evidence-based psychological intervention can positively impact post-TKA sequelae. This study aims to pilot the effectiveness of an empirically supported intervention, mindfulness based stress reduction (MBSR), on post-TKA outcomes using a superiority randomized controlled trial (RCT) design.

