Preliminary Surgical-Related Outcomes. Despite this compelling evidence, there is little research examining MBSR in surgical contexts. One preliminary study investigating MBSR postoperatively following a spontaneous subarachnoid hemorrhage surgery found it resulted in significant decreases in ratings of depression and physical

stress, suggesting it was successful in both reducing psychological symptoms and improving homeostasis control mechanisms of the autonomic nervous system (37).

(b) General Overview of the Research Plan

The current research will consist of a pre-surgical MBSR course compared to a treatment-as-usual condition to evaluate post-surgical outcomes, including post-operative pain (severity and catastrophizing), improved physical functioning (interference and illness impact), post-surgery complications, and psychological factors including enhanced quality of life, reduced emotional distress (anxiety and depressive), enhanced cognitive skills, and improved sleep. The data will reveal if MBSR is feasible in a TKA population and determine if there are post-surgical benefits, as compared to the treatment as usual (TAU) group.

(c) Objectives, Research Design, and Hypotheses

Objective: The primary objectives are (a) to determine if an 8-week pre-operative MBSR program is feasible in a TKA population, and (b) to determine if this program results in reductions in post-operative pain (pain behavior, pain catastrophizing), improved physical functioning (pain interference, psychosocial illness impact), enhanced quality of life (global health), reduced emotional distress (anxiety and depression), enhanced cognitive skills (Cognitive Concerns), and improved sleep (fatigue, sleep disturbance) compared to TAU.

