Research Design: Forty-five participants on the waitlist for a TKA will be recruited from Concordia Hospital Hip and Knee Institute – a facility that performs 800 TKA's per year. Participants will be divided into two groups: the MBSR group prior to surgery (30 participants, divided into two MBSR groups), and the TAU (15 participants; MBSR after surgery). The individuals in the MBSR group will receive a pre-operative 8-week community-based MBSR course, which includes group classes lasting 2.5 hours a week, 45-minutes of home practice 6 days per week, a 1-hour orientation session at the beginning, and a full-day silent retreat at the end. During the orientation, participants will complete the study measures for this study. Two weeks prior to the surgery at the pre-anesthesia clinic, patients will receive another short self-reported questionnaire between the MBSR intervention and TAU groups. Patients will subsequently receive post-operative questionnaires at the following regularly scheduled post-operative appointments: 6-8 weeks after surgery, and at 6 month and 1 year follow-ups. Clinic personnel, who are blinded to assignment, will administer these measures with all other regularly distributed clinical measures. Clinic personnel will also review the chart to inform researchers as to what physical condition contributed to the need for a TKA. The TAU group will have the opportunity to enroll in an MBSR course following the completion of the study (after approximately 1 year), at no cost.

Hypotheses: We predict that pre-operative MBSR will improve post-surgical outcomes including reductions in post-operative pain (pain behavior, pain catastrophizing),

improved physical functioning (pain interference, psychosocial illness impact), enhanced quality of life (global health), reduced emotional distress (anxiety and depression), enhanced cognitive skills (Cognitive Concerns), and improved sleep (fatigue, sleep disturbance) compared to TAU group.

MBSR is an empirically-supported intervention that has been used to examine various health outcomes and psychological factors in both health conditions (e.g., chronic pain; 29, anxiety and depression; 28, and binge and emotional eating; 32) and more recently, surgical populations (spontaneous subarachnoid hemorrhage surgery; 37). We are therefore confident that MBSR will improve the psychological factors and the physical health factors we described above.

(d) The Selection of Participants / Sample Size Calculations

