TKA patients will be recruited from the TKA waitlist at Concordia Hospital Hip and Knee Institute— a facility that performs 800 TKA's per year. A Concordia Hospital Hip and Knee Institute staff member or a psychology graduate student on the project will contact all participants, ensuring the inclusion/exclusion criteria are met. Participants will be ensured that their participation is completely voluntary, and will be reminded that assignment to treatment conditions is completely random; therefore, participants will not feel obligated to participate, but will know receiving MBSR before their surgery is not guaranteed.

The sample size was estimated based on G*Power statistical software using a 2:1 approach with a large effect size (Cohen's $d = 0.8$). We will recruit 30 patients for the intervention where they will be divided in 2 groups that will consecutively run. The third TAU group will include 15 patients. This will yield 45 total participants. A 2:1 approach is used to assess within person change pre- and post-surgically given the pilot nature of the study and to protect against up to 20% attrition in the intervention group.

(e) Behavioural and Diagnostic Data

A variety of data will be collected during the initial telephone screening to ensure that participants meet our inclusion criteria. A phone screen template will be used to standardize the recruitment process. Because phone screening is conversational, the study description on the phone screen form has phrases that are italicized, and these are the key points that the phone screen interviewer will convey. We will be collecting information about age, sex, and language that they can read and understand. We will ask whether they are currently on the waitlist for a TKA, and whether the surgery they are waiting for is their first surgery (i.e., not a revision surgery). We will also be asking whether participants have ever been enrolled in an MBSR program or any other mindfulness course before, and if so, when it took place. All of these questions are very important in deciding whether participants are eligible for participating in this study.

After participants are screened for eligibility and provide verbal consent, they will be mailed out packages explaining MBSR in more detail, include two copies of consent forms, and a return envelope. After randomization, those in the MBSR group will complete study measures prior to their pre-operative MBSR course (at an orientation

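### The SAP puts its focus on paired t-tests inside the MBSR arm, which cannot answer the comparison with TAU; the comparison that can is left without a visit or a stated use of baseline.

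*SAP*

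**What the plan says.** Protocol section 1(a) describes a pilot "using a superiority randomized controlled trial (RCT) design". In section 1(c), objective (b) lists the outcome domains and ends with "improved sleep (fatigue, sleep disturbance) compared to TAU", so it is a comparison between arms.

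The SAP repeats Protocol section 1(f) and has three sentences. The first names two contrasts: "We will be looking at changes in outcomes from before to after the MBSR intervention in (a) the MBSR compared to TAU participants", and then change within the MBSR participants. The second sets the emphasis: "We will focus on within-persons mean differences using paired samples t-tests within the intervention group". The third reads "To determine the impact of MBSR on the postoperative TKA outcomes, we will conduct multivariate analyses of variance of conceptually linked dependent variables", with Tukey tests to follow a significant result.

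Section 1(d) gives a reason for the unequal allocation: "A 2:1 approach is used to assess within person change pre- and post-surgically given the pilot nature of the study".

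Section 1(c) schedules measures at orientation, at the pre-anaesthesia clinic two weeks before surgery, and at 6-8 weeks, 6 months and 1 year after surgery. On baseline it says "During the orientation, participants will complete the study measures for this study". Section 1(e) describes the pre-course measures for the MBSR group only, after randomisation.

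**The concern.** Only the randomised comparison can answer objective (b). The declared focus is an analysis without a comparator, so a change that would also have occurred under TAU could be reported as an effect of MBSR. In patients waiting for and then recovering from knee replacement, such a change is plausible.

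The comparison that could answer the objective is thinly specified. With three postoperative visits and none named for the MANOVA, the visit could be chosen after the data are seen. Nor is it stated how the pre-course score enters. It is unclear whether TAU patients give a pre-surgical score at all, and one that was not collected cannot be recovered later.

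**Working it through.** **1. Which visits form the pair, and who has a baseline.** The SAP speaks of change across the MBSR course. That could mean orientation to the pre-anaesthesia clinic, with no surgery in between, or orientation to a postoperative visit. Section 1(d) speaks of change before and after surgery. Neither names visits.

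For the TAU baseline there are four pieces of text. Section 1(c) says participants in general complete measures at orientation. Section 1(e) says so only for MBSR. The budget in section 1(i) pays for orientation meetings for all three groups and mentions mailed pre-operative packages. Section 1(c) places TAU's course about a year later, so TAU's orientation may fall after surgery. Together these do not settle the matter.

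**2. The plan's own figure.** Section 1(d) gives d = 0.8, 2:1 allocation and 45 patients (30/15), without alpha, sidedness or power. For a two-sample t-test the noncentrality is 0.8 × √(30×15/45) = 0.8 × √10 = 2.530 with 43 df.
- One-sided 0.05: power 0.801, and 45 is the smallest 2:1 total that reaches 80%.
- Two-sided 0.05: power 0.696; 80% would need 60.

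So 45 is consistent with a between-arm calculation at one-sided 0.05 (or two-sided 0.10) and 80% power. That is an inference, because the section does not name the test.

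**3. How often the paired test is significant when MBSR does nothing.** Assume that both arms shift by the same amount (in SD units), with correlation r between the two scores. The documents give neither value. Then dz = shift/√(2(1−r)), noncentrality = dz × √n, df = n−1, two-sided 0.05. Here n is 30, or 30 × 0.8 = 24 after the 20% attrition in section 1(d). Example: shift 0.5, r = 0.5, n = 30 gives dz = 0.5/√1 = 0.5, noncentrality 0.5 × √30 = 2.739 and probability 0.754.

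| Common shift | n | r = 0.3 | r = 0.5 | r = 0.7 |
|---|---|---|---|---|
| 0.1 SD | 24 | 0.068 | 0.076 | 0.093 |
| 0.1 SD | 30 | 0.073 | 0.083 | 0.105 |
| 0.2 SD | 24 | 0.125 | 0.156 | 0.228 |
| 0.2 SD | 30 | 0.146 | 0.185 | 0.277 |
| 0.5 SD | 24 | 0.509 | 0.650 | 0.857 |
| 0.5 SD | 30 | 0.609 | 0.754 | 0.927 |

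**4. The between-arm test in the same situation.** A shift common to both arms cancels in the difference. In a simulation of 20,000 trials (30/15, r = 0.5, shift 0.5 SD, independent patients), the paired test was significant in 75.2% and the between-arm test of change in 4.9%.

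**5. Power of the comparison the objective needs.** At d = 0.8 and two-sided 0.05 (assumed), unadjusted:
- 30/15: noncentrality 2.530, power 0.696.
- 24/15: 0.8 × √(24×15/39) = 2.431, power 0.658.

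ANCOVA at an assumed r = 0.5 has effect 0.8/√(1−0.25) = 0.924 and df = N−3:
- 30/15: noncentrality 2.921, power 0.814.
- 24/15: noncentrality 2.807, power 0.780.

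These figures ignore clustering by course group.

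**The case against.** The best defence is that the focus sentence is confined to the intervention group, so it may simply give the method for the second of the two contrasts. The next sentence assigns the causal question to the MANOVA. Nothing says a paired result will be offered as evidence against TAU. The study is a pilot, feasibility is objective (a), and section 1(d) ties the within-person aim to the pilot purpose.

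Much of this stands, and it rules out three stronger readings.
- A reader might infer that the SAP omits the between-arm comparison or ignores baseline. It does not: it names MBSR versus TAU, and comparing changes can be read as using change scores. What is missing is any statement that the MANOVA uses change scores or a covariate, and at which visit.
- A reader might infer that section 1(d) and the SAP contradict each other on the window. They need not: section 1(d) justifies the allocation and may mean change at both pre-operative and postoperative visits. The defect is that the visits are unnamed.
- A reader might infer that TAU has no baseline. The budget line on orientation for all three groups points the other way, without settling it.

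The defence does not remove the word focus, or the fact that objective (b) is itself listed as primary and is comparative. Pilot status supports describing within-arm change; it does not let that change answer a question about TAU.

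**Conclusion.** The point holds and should be fixed. The stated emphasis is on an analysis that cannot answer objective (b), and the analysis that can is under-specified.

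The size depends on a shift the documents do not give. The risk is slight if both arms change by 0.1 SD (about 7-11%), moderate at 0.2 SD (13-28%) and large at 0.5 SD (51-93%). Nothing in the documents supports 0.5 SD in particular, least of all if the window ends before surgery. A reader might take these percentages for an inflated type I error of the paired test. They are not: the test correctly detects a real change that MBSR did not cause. The error would lie in attributing that change to MBSR.

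**What to change.** Replace the focus sentence, in the SAP and in Protocol section 1(f), with:

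> Statements about the effect of MBSR rest on the MBSR-versus-TAU difference by assigned arm at one named primary postoperative visit, adjusted for the pre-course score (ANCOVA), with 95% CI; other visits are secondary. Within-arm changes between named visits are descriptive, are given for both arms, and are not evidence of an MBSR effect.

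If the MANOVA is kept, state its visit and how baseline enters it. State that both arms complete the same baseline questionnaires before the MBSR course, preferably before randomisation. If TAU turns out to have no baseline, compare follow-up scores between arms unadjusted.

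The cost is wording and possibly one extra questionnaire for 15 TAU patients. Fewer results will be significant. Under the assumptions above, between-arm power is 70% at 30/15 and 66% at 24/15 unadjusted, and about 81% and 78% with ANCOVA, so collecting the TAU baseline recovers part of what is lost.

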session). These measures include: Patient- Reported Outcomes Measurements Information System (PROMIS) scales (Cognitive function, Fatigue, Pain Interference, Pain Behavior, Sleep Disturbance, Psychosocial Illness Impact, Global Health, Anxiety, and Depression scales (see: www.healthmeasures.net for information pertaining to NIH PROMIS initiative), a demographics form, the 13- item Pain Catastrophizing Scale (38), and the Five Facet Mindfulness Questionnaire (41). Two weeks prior to the surgery at the pre-anesthesia clinic, patients will receive another short self-reported questionnaire, as well as a questionnaire asking about participation in any other prehabilitation courses offered through the Hip and Knee Institute or any other centre. In PAC, clinic personnel will review the chart to inform researchers as to what physical condition contributed to the need for a TKA. Patients will subsequently receive post-operative questionnaires at the following regularly scheduled post-operative appointments: week 6-8, 6 month, and 1 year. Clinic personnel, who are blinded to assignment, will administer these measures with all other regularly distributed clinical measures, and they can complete while waiting for their appointment.

(f) Data Analysis

We will be looking at changes in outcomes from before to after the MBSR intervention in (a) the MBSR compared to TAU participants, and (b) within the MBSR participants. We will focus on within-persons mean differences using paired samples t-tests within the intervention group. To determine the impact of MBSR on the postoperative TKA outcomes, we will conduct multivariate analyses of variance of conceptually linked dependent variables (i.e. pain variables, mental health variables) with significant results followed up by Tukey post-hoc tests.

(g) Timeline

We hope to begin recruitment after we have obtained ethics approval from both the University of Manitoba and Concordia Hospital Hip and Knee Institute in August 2017. We hope to run the MBSR courses in Fall 2017, run by a teacher ([name]) with extensive MBSR and yoga training. We anticipate the total duration of this study will August 2017 to August 2019. We will renew our ethics protocol annually, as per HREB requirements.

(h) Definition of Adverse Events

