The adverse events should be limited to a reaction to the MBSR course. Participants will be fully informed about MBSR, and what participation in the course will include. In the unlikely event that a participant feels extreme discomfort in a meditation position (e.g., their knee hurts too much), the MBSR instructor has been trained to manage these situations. If additional support is warranted, appropriate resources will be implemented as described in the ethics form.

(i) Budget

Professional Assistance:

MBSR instruction:

\$18,500 in fee payment to qualified MBSR instructor.

$[(45 \text{ participants} \times \$400/\text{participant}) + \$500 \text{ orientation fee} = \$18,500]$

A certified, trained MBSR instructor is required to deliver the MBSR course. The course will be offered to the TKA patients at no cost to themselves, so as to maximize enrollment. No honorariums will be provided to the participants, as the waiver of the MBSR fee is already significant. The MBSR instructor's time, her securing of accommodations in which to hold the sessions, and providing all necessary resources (i.e., workbooks) are included in the fee of \$400/participant. The instructor's time for conducting the 1 hour orientation meetings for all 3 groups is \$500.

See letter from MBSR instructor for quote (appended to this application).

TKA clinic assistance:

$[(\$60/\text{hr} \times 143 \text{ hrs}) + \$150] = \$8,730$

\$8,730 is required for the assistance of the TKA clinic staff. As TKA patients will be recruited from the clinic, access to standard clinic measures will be required, and administration of the additional study-specific measures will be performed by clinic staff at the patient's scheduled appointments, compensation to clinic staff is required. Clinic staff have identified the following time commitments:

1. Pulling waitlist patient info (contact #'s & expected date of sx): 4 hrs
2. Query to pull pre-op Oxford (and other) data for 30 pts: 4 hrs
3. Administer, fill & send post-op questionnaire packages at 6 wks, 6 mo, 12 mo: $\frac{1}{2}$ hr per visit = 45 hrs
4. Query to pull all post-op Oxford, Satisfaction data for 30 pts: 30 hrs
5. Calling and recruiting of patients (mail-out consent & pre-op packages) $\frac{1}{2}$ hr per patient (say 25% rate of enrollment) + mailing costs (~\$5 per, incl. return shipping) = 60 hrs + \$150 mailing

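### Arms are compared by MANOVA with no baseline covariate, and a TAU baseline is not clearly scheduled; collecting one in both arms and adjusting for it usually adds precision

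*SAP*

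**What the plan says.** **Analysis.** The SAP, whose text Protocol 1(f) shares, sets out to examine "changes in outcomes from before to after the MBSR intervention in (a) the MBSR compared to TAU participants". For the between-arm test it says "To determine the impact of MBSR on the postoperative TKA outcomes, we will conduct multivariate analyses of variance of conceptually linked dependent variables", followed by post-hoc tests. Neither document names a covariate, says whether change or post-operative scores enter the MANOVA, or names the visit.

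**Baseline, MBSR arm.** Protocol 1(e) is explicit: "After randomization, those in the MBSR group will complete study measures prior to their pre-operative MBSR course".

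**Baseline, TAU arm.** No sentence dates it. Four places bear on it:
- Protocol 1(c), Research Design: "During the orientation, participants will complete the study measures for this study". The same paragraph lists the orientation as a component of the MBSR course.
- Protocol 1(c) also says that patients get 'another' questionnaire at the pre-anesthesia clinic two weeks before surgery, and mentions both groups.
- Protocol 1(c) on the TAU course: "The TAU group will have the opportunity to enroll in an MBSR course following the completion of the study", which it puts at about 1 year.
- Protocol 1(i) pays for the instructor's "time for conducting the 1 hour orientation meetings for all 3 groups", for mailed pre-op packages of unstated content, and for a query of pre-op Oxford and other data for 30 patients.

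**The concern.** A between-arm comparison of changes needs a pre-course score in both arms. If TAU has none, that comparison cannot be done, and a baseline that was not collected cannot be recovered later. If TAU has one, the plan still does not say how it is used. Either unadjusted reading, change scores or post-operative scores, usually gives a wider interval than adjusting for the baseline. The two readings can also differ a good deal in power, and nothing in the plan stops the choice from being made after the data are seen. The between-arm comparison is primary objective (b) in Protocol 1(c), and TAU has only 15 patients.

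**Working it through.** **Inputs from the documents.** d = 0.8; 2:1 allocation, 30 + 15 = 45; up to 20% attrition in the MBSR arm, so 24:15 (Protocol 1(d)).

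**Assumptions, because the documents give none.** Alpha 0.05; power 80% where a sample size is solved for; r = 0.3/0.5/0.7; equal SDs before and after; d in post-operative SD units unless stated.

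**1. The plan's own figure.** By the noncentral t, one-sided alpha 0.05 gives power 0.801 at 30:15, which reproduces 45. Two-sided power at 30:15 is 0.696. Two-sided 80% needs 60 (40:20 gives 0.819; 38:19 gives 0.799).

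**2. One scale, 30:15, two-sided.** Noncentrality = d_eff × √(30×15/45) = d_eff × √10.
- Post-operative scores: d_eff = 0.8, df 43.
- Change scores: d_eff = 0.8/√(2(1−r)), df 43. This is 0.676/0.800/1.033.
- Adjusted: d_eff = 0.8/√((1−r²)×42/41), df 42. This is 0.829/0.913/1.107. The factor 42/41 is the average cost of estimating the slope.

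| Analysis | r = 0.3 | r = 0.5 | r = 0.7 |
|---|---|---|---|
| Post-operative | 69.6% | 69.6% | 69.6% |
| Change | 55.2% | 69.6% | 89.1% |
| Adjusted | 72.6% | 80.5% | 92.8% |

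At 24:15 the adjusted figures are 68.6/76.8/90.4%, against 65.8% (post-operative) and 51.6/65.8/86.3% (change). One-sided at 30:15 they are 82.5/88.4/96.4%, against 80.1% and 67.7/80.1/94.2%.

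95% CI half-width at 30:15, post-operative scores: 2.017 × √(1/30 + 1/15) = 2.017 × 0.316 = 0.64 SD. Adjusted: 0.62/0.56/0.46 SD. Change: 0.75/0.64/0.49 SD.

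**3. When adjustment has the smaller variance.** Against post-operative scores: (1−r²)(42/41) < 1, so r² > 1/42 and r > 0.154. Against change scores: (1−r²)(42/41) < 2(1−r), so 1 + r < 82/42 and r < 0.952. At r = 0, adjusted power is 68.5%, a loss of 1.1 points.

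**4. If d is in change-score SD units instead.** The post-operative d becomes 0.8√(2(1−r)). Change-score power is then 69.6% at every r, and adjusted power is 85.7/80.5/75.4%. The ranking holds but the trend with r reverses.

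**5. Families of p scales, 30:15, two-sided, all d = 0.8.**
- Unadjusted: Hotelling T², noncentral F(p, 44−p), with λ = 10·d′R⁻¹d = 10 × 0.64p/(1+(p−1)ρ), where ρ is the correlation between scales.
- All baselines entered: F(p, 44−2p), with λ/(1−r²)/(1+T²/43), averaged over the chance baseline T².

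Power for ρ = 0.3 / 0.5:

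| Scales | Post-operative | Adjusted, r = 0.3 | Adjusted, r = 0.5 | Break-even r |
|---|---|---|---|---|
| 2 | 77.8 / 71.4% | 79.7 / 73.4% | 87.1 / 81.7% | about 0.22 |
| 3 | 80.0 / 69.6% | 80.6 / 70.3% | 88.1 / 79.3% | about 0.28 |
| 4 | 80.1 / 66.9% | 79.3 / 66.1% | 87.3 / 75.6% | about 0.32 |

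At r = 0.5 the gain is about 7 to 10 points throughout. With four scales at 24:15 and r = 0.3, adjustment loses nearly 2 points (73.6 against 75.5%; 60.1 against 61.9%).

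**The case against.** The best defence is that a TAU baseline is probably intended. 'Another' questionnaire implies an earlier one, participants in general are said to complete measures at orientation, orientations are paid for in all three groups, and pre-op packages are mailed. A reader might nonetheless infer that TAU has no baseline at all; the documents do not support that. They also do not settle the matter. The orientation is described as part of a course that TAU takes about a year later, the contents of the packages are not given, and the data query covers 30 patients of unstated arm and names Oxford data, which is not a listed outcome. What stands is a gap in what and when.

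The second defence is that this is a pilot focused on within-person differences, that r is unknown, and that the unadjusted test is valid. Validity is conceded: a reader might take the missing covariate to bias the comparison, but under randomization it does not. The uncertainty about r also stands, and it bites harder in larger families. A claim that adjustment always gains would be wrong: three scales roughly break even at r = 0.3, and four lose slightly. It does not remove the point, because the plan makes the between-arm comparison a primary objective and leaves its outcome undefined whatever r is.

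**Conclusion.** The point holds as a gap in specification and a usual loss of precision; it is a cheap improvement. A TAU baseline is suggested but not scheduled, and the between-arm model does not say how a baseline enters. For one scale at 30:15, adjustment gains about 3, 11 and 23 points of power over post-operative scores at r = 0.3, 0.5 and 0.7, and costs about 1 point at r = 0. At r = 0.5 either unadjusted reading would need 60 patients at 2:1 to match what adjustment gives with 45. These sizes rest on assumed alpha, sidedness, r, equal SDs and the scale on which d is expressed. The ranking for one scale survives a change in the scale of d; the individual figures do not. A reader might also infer that 45 is simply too few. That does not follow from this point, because sidedness and power are unstated and a one-sided 5% test reproduces 45.

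**What to change.** 1. State that both arms complete the existing pre-course measures at the same point, preferably before randomization. One route is the mailing that Protocol 1(e) says will already "include two copies of consent forms, and a return envelope", with the measures completed after the consent form is signed.
2. Name the post-operative visit (6-8 weeks, 6 months or 1 year) whose score is the between-arm outcome.
3. Estimate the MBSR-TAU difference for each scale by ANCOVA on that scale's own baseline, with a 95% CI in scale units.
4. If a multivariate test is kept, keep the families small, because entering every baseline costs degrees of freedom.
5. Do not use the pre-anesthesia questionnaire as the baseline. It follows randomization and appears to follow the course in the MBSR arm.
6. If no TAU baseline can be collected, compare post-operative scores only and remove the between-arm comparison of changes.

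**Cost.** If no TAU baseline is now planned, this is a change of conduct as well as analysis. Postage: Protocol 1(i) allows $150 at about $5 each, so 30 packages; covering all 45 adds 15 × $5 = $75. Staff time, if handled like the post-operative packages: 15 × ½ hour × $60 = up to about $450, in a budget already $2,230 over its limit. One degree of freedom is lost per covariate. There is little or no gain if r is low, and a baseline mailed well before the course may lower r.

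### The only between-arm analysis is MANOVA with no missing-data method, so patients with incomplete outcomes drop out of it and score-related loss in the MBSR arm would bias it

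*SAP*

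**What the plan says.** The SAP is a single paragraph, repeated in Protocol 1(f) Data Analysis. It opens: "We will be looking at changes in outcomes from before to after the MBSR intervention", both between arms and within the MBSR arm. The within-arm method is clear: "We will focus on within-persons mean differences using paired samples t-tests within the intervention group". The only method for the between-arm question is that "we will conduct multivariate analyses of variance of conceptually linked dependent variables", with pain and mental health given as example families and Tukey tests after a significant result. Neither document names the visit tested, a time factor, covariates, an analysis set or a treatment of missing data.

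Protocol 1(c) schedules post-operative questionnaires at "6-8 weeks after surgery, and at 6 month and 1 year follow-ups". Protocol 1(e) lists nine PROMIS scales plus the Pain Catastrophizing Scale and a mindfulness questionnaire. Protocol 1(d) sets 30 MBSR and 15 TAU patients and explains the 2:1 ratio partly as a way "to protect against up to 20% attrition in the intervention group". It makes no matching allowance for TAU.

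**The concern.** Standard MANOVA needs a value for every dependent variable in the family. With no imputation planned, a patient who lacks one scale is lost from the whole family. A patient seen at 6-8 weeks but not at 1 year adds nothing to a 1-year test. The possible readings of the plan share this. A single-visit MANOVA needs all scales at that visit, a change-score MANOVA needs both time points, and a repeated-measures MANOVA needs every visit.

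The greater risk is bias. If MBSR patients who are doing worse are less likely to return later questionnaires, those who remain look better than the arm as randomised. The trial could then show a benefit that MBSR did not produce. The protocol foresees loss in one arm only, which is the pattern in which this bias does not cancel between arms.

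**Working it through.** **1. The plan's own figure.** Inputs from Protocol 1(d): d = 0.8, 2:1, 30 and 15. Alpha, sidedness and power are not stated. With n(TAU) = (1 + 1/2)(z_α + z_β)²/d², one-sided α = 0.05 and 80% power:

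1.5 × (1.645 + 0.842)²/0.64 = 14.5, rounded up to 15. This gives 30 + 15 = 45.

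So 45 is reproduced under one standard choice, with no attrition allowance in it. The figure is not shown to be wrong.

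**2. Power lost if six MBSR patients are lost.** 20% of 30 is 6, leaving 24. Univariate t-test with noncentrality d√(n₁n₂/(n₁+n₂)) and assumed α = 0.05:

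| MBSR:TAU | Noncentrality | df | Power, two-sided | Power, one-sided |
|---|---|---|---|---|
| 30:15 | 0.8√(450/45) = 2.53 | 43 | 0.70 | 0.80 |
| 24:15 | 0.8√(360/39) = 2.43 | 37 | 0.66 | 0.77 |

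The loss is 3 to 4 points.

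**3. Listwise loss across scales.** The documents give neither the number of scales per family nor a missingness rate, so this step is illustrative. With three scales each missing 5% independently, 0.95³ = 85.7% of patients are complete, and 24:15 becomes about 21:13. MANOVA power (Hotelling T², d = 0.8 on each scale, correlation 0.5) is 0.70 at 30:15, 0.65 at 24:15 and 0.57 at 21:13. Scales are handed out together, so missing values may cluster in the same patients, and the loss would then be smaller.

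**4. Bias with no true effect.** Let X be an earlier score in SD units, with higher meaning worse. MBSR dropout follows logit P = a + bX, with a set to give the chosen overall rate. TAU is complete. The later outcome has correlation ρ with X. The retained MBSR patients have mean m = E[X(1−P)]/E[1−P], and the complete-case difference is biased by ρm.

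| Dropout | Slope b | m | ρ = 0.3 | ρ = 0.5 | ρ = 0.7 |
|---|---|---|---|---|---|
| 20% | 0.5 | −0.10 | −0.03 | −0.05 | −0.07 |
| 20% | 1.0 | −0.17 | −0.05 | −0.09 | −0.12 |
| 20% | 1.5 | −0.23 | −0.07 | −0.11 | −0.16 |
| 22% | 0.5 | −0.11 | −0.03 | −0.05 | −0.07 |
| 22% | 1.0 | −0.19 | −0.06 | −0.09 | −0.13 |
| 22% | 1.5 | −0.25 | −0.07 | −0.12 | −0.17 |

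Negative values favour MBSR. Dropout rate, slope and correlation are all assumptions. The top of the range is demanding: at 22% and slope 1.5, about 4% drop out at 1 SD better than average and 44% at 1 SD worse.

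**5. What a mixed model would change.** Simulation of 500 runs: one scale, 30:15, three post-operative visits, baseline covariate, within-person correlation 0.5, about 25% MBSR-only dropout driven by the last observed score.

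| True effect | Complete cases: estimate, rejection | Mixed model: estimate, rejection |
|---|---|---|
| 0 | −0.11 SD, 8.0% | +0.01 SD, 4.2% |
| −0.80 | −0.90 SD, 73.8% | −0.80 SD, 74.8% |

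The Monte Carlo error of a 5% rejection rate is √(0.05 × 0.95/500), about 1 point. The gain is in bias; power is almost unchanged.

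**The case against.** Several stronger readings are tempting, and the documents do not support them.

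- **A reader might infer that each visit is analysed in isolation.** The plan names no visit. Variables are grouped by concept, which makes separate visits the likelier reading, but the opening reference to change leaves room for change scores or a time factor. What is established is that the time structure is unspecified and that none of these MANOVA readings uses partial follow-up.
- **A reader might infer that the plan expects 20% attrition.** It gives an upper limit to guard against, not a forecast. Leaving the course also need not mean losing outcome data, because clinic staff hand out the questionnaires at routine post-surgical visits.
- **A reader might say that the plan prescribes deletion.** It does not. Deletion is what standard MANOVA does when no other rule is given.
- **A reader might claim a serious loss of power.** Two-sided power near 0.50 requires 20% loss in TAU as well (24:12), which the documents never mention, plus 5% independent missingness on each of four scales. The loss that the plan itself allows for costs 3 to 4 points.

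It is also fair to say that this is a 45-patient pilot with feasibility as its first objective, that bias arises only if loss is related to outcome, and that a mixed model gives up the family-level test. All of this stands and limits the size of the point. It does not remove it: efficacy against TAU is also a primary objective, and the one analysis that addresses it has no defence against informative loss.

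**Conclusion.** The concern holds in a limited form. With MANOVA as the only between-arm method and no missing-data rule, patients with an incomplete outcome vector fall out of the comparison and partial follow-up is unused. If 20-22% of MBSR patients are lost in relation to earlier scores, the null bias is about 0.03 to 0.17 SD in favour of MBSR, under the assumed correlations and slopes. If loss is unrelated to outcome, there is no such bias.

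Power is a minor argument: 0.70 to 0.66 (two-sided, univariate t, d = 0.8) for the loss that the plan allows for. Anything beyond that depends on a missingness rate that the documents do not give. The case for change therefore rests on bias. The sponsor should make the change, though it is not critical for a pilot of this size.

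**What to change.** Make the between-arm analysis one linear mixed model per outcome, with arm, visit (6-8 weeks, 6 months, 1 year) and arm-by-visit. Use all observed post-operative data, analyse every randomised patient by assigned arm, and report the arm difference with a 95% CI at each visit. Name one lead outcome and visit. Keep MANOVA as a supportive complete-case analysis, and state which visit and which scales each family covers.

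Add a baseline covariate only if it is collected in both arms. Protocol 1(e) states the pre-course measures for the MBSR group only, and the later pre-anesthesia questionnaire comes after randomisation, so it is not a substitute.

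The cost is SAP wording and slightly more analysis work, with no new patients or visits. There are three downsides. Inference is per outcome rather than per family, hence the need for a named lead. The bias is removed only under missing-at-random given the scores in the model, so loss driven by a pre-course score that is left out would still bias the result. Patients with no post-operative data are not recovered.
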